5.4.2.6 Table of Assessments and Procedures to be Performed Throughout the Study

See Appendix C.

5.4.3 Prior and Concomitant Medications

Throughout the study duration, and two weeks leading up to randomization, patients are not permitted to receive other sources of iron supplementation, including but not limited to, other oral ferrous tablets and intravenous iron therapy.

Patients should be advised not to take oral iron within 2 hours of antibiotics, bisphosphonates³⁹, levodopa, methyldopa⁴⁰, mycophenolate mofetil⁴¹, or thyroid medication⁴².

5.4.4 Participant Compliance Monitoring and Assessment

Throughout the study duration, patients' compliance with ingesting their oral iron tablets will be monitored through a personal patient diary, through direct contact between the patient and research coordinator/assistant at designated assessment times and a pill count following the 12 week supplementation period. Patients will have the opportunity to check-off when they have taken their tablet on the calendar pages of their patient diary, which indicate which days they should be ingesting the oral ferrous sulfate. At the first, fourth, and eighth weeks after beginning the study treatment, patients will either be called or emailed to assess patient adherence.

If a patient misses a pill, they will continue with the next dose as directed on the calendar and will be advised not to double up dosing.

Lastly, at the end of the 12 week supplementation period, patient will return the patient diary, the pill bottle provided to them and any unused tablets for a final pill count; this number is compared to the number of tablets the patient should have ingested during the 12 weeks.

5.4.5 Protocol Deviations

Planned or unplanned deviations may occur on the part of the participant, the investigator, or study research team. In resolution to a deviation, corrective/preventative actions are to be developed and implemented in a timely manner. Protocol deviations will be documented and reported as required and assessed where necessary during analysis.

6.0 STORAGE AND DISPENSATION OF FERROUS SULFATE

Pharmacy will dispense a 3 month prescription for each group (see Supporting Documents). The patient must keep the drug at room temperature.

7.0 CRITERIA FOR OUTCOME ASSESSMENT

7.1 Primary outcome assessment

Feasibility: Enrollment in the trial will be defined as documentation of informed consent for patients approached

If the study is unable to enroll 52 patients in a 2 year enrolment period, the study as it is currently designed will not be deemed feasible.

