5.3 Study Activities

5.3.1 Patient recruitment, consent, screening and enrolment

Patients meeting inclusion criteria will be identified through referring clinician offices (hematology and primary care physicians). Initial contact about the study will be made by a health care provider from the patient's clinical team. Study personnel will approach the MRP for permission to approach the patient or ask that they introduce the study to the patient. With permission to enter the patient's circle of care, the research coordinator will then approach potentially eligible patients. The research coordinator will introduce the trial, confirm eligibility and conduct the informed consent discussion. The study personnel will screen patients for exclusion criteria by asking about the patient's medical history and reviewing their bloodwork that will be taken as a standard of care when visiting the MRP. Patients interested in participating and meeting both inclusion and no exclusion criteria will be given an Informed Consent Form. This discussion will include the rationale for the study, the anticipated risks and benefits of participation, and their rights as a study participant (including withdrawal at any time). Capable participants will be offered an opportunity to ask questions and consult with their family and/or their physician before enrollment. If the patient is deemed incapable of providing informed consent for the study, study personnel will approach the patient's physician to determine if it is safe to delay treatment while a substitute decision maker is identified and approached. As the initiation of oral iron is not urgent, there will be enough time to assess the patient for inclusion in the study before initiating treatment. The subject will be invited to participate and must provide informed consent prior to any study related procedures. One signed copy of the informed consent will be placed in the participant's medical record, another copy given to the participant and the original kept in the study file with the research coordinator. Once the subject is enrolled, his/her family physician will be informed about

his/her participation in the study. If the participant does not wish to participate, the reason for declining will be documented. Patients will be identified by initials only on the screening log.

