Another potential recruitment site will be through Canadian Blood Services. Blood donors that have been deferred due to low hemoglobin levels (within the local Toronto area close to hospital study sites) will be provided with a letter (see Supporting Documents) which explains that the donor was deferred and for the donor to see visit their family physician for further investigation. In addition, a letter to the family physician will explain key points about the study purpose, rationale, procedures and detailed information about the DEODO trial. If the patient is interested in participating in the study, after visiting their family physician, the family physician can refer the patient to one of the study sites. The letter contains contact information for the Principal Investigator and Research Coordinator if the patient or their family physician has any questions. It is also acceptable for the patient to contact the study site directly in which case permission from the MRP is not required. Once the patient is referred to or has contacted a study site, then consent will occur as outlined in the previous paragraph.

Once the patient has consented, bloodwork will be performed at the participating institution's laboratory or at a local lab, if it has not been performed in the past 2 weeks. Eligibility of the patient will be determined. If the eligibility is confirmed, then the patient will be enrolled (assigned a study ID) and randomized. Any additional bloodwork required within the pre-specified time frame (see 5.4.1.2) can be drawn or added on to the bloodwork already completed.

All sites will obtain Research Ethics Board (REB) approval of the protocol and the informed consent form. A recruitment log of eligible and ineligible patients as well as reasons for non-consent will be kept at each participating centre. We anticipate that this study will take 2 years to complete.

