5.3.3.4 Treatment Assignment Procedures

Once enrolled, patients will be randomized to either the daily, or every other day treatment arm through the randomization procedure described in section 5.3.2.

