APPENDIX C:

Table 1: Flow Chart of Assessments/Procedures to be Performed Throughout the Study

Procedures	Prior to Enrolment	After Enrolment	Week 1 (±3 days)	Week 4 (±7 days)	Week 8 (±7 days)	Week 12 (±7 days)	Week 13 (7 days ± 3 days after final study visit)
Referring clinician offices identify potential patients as participants	X						
Patient (surrogate) informed consent	X						
Inclusion and exclusion criteria	X						
Randomization		X					
Baseline Data							
Case Logs (reason for lack of consent, protocol violations)	X						
Medical History		X					
Laboratory Assessments							
Hemoglobin	X			X		X	
Reticulocyte Count	X			X		X	
C reactive protein (CRP) – acute phase reactant	X						
Ferritin	X					X	
Serum Iron	X					X	
Transferrin Saturation (TSAT)	X					X	
Creatinine clearance	X						
Subjective Patient Assessments							
FACIT-Fatigue Scale Questionnaire		X		X	X	X	
Patient Diary Adherence			X reminder	X	X	X	
Side Effect Questionnaire				X	X	X	
Pill Count						X	
Adverse and Serious Adverse Events			X	X	X	X	X
Need for Therapy Escalation			X	X	X	X	

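### Section 7.1 counts enrolment at consent, but 5.3.1, 5.3.3.4 and Appendix C place it after consent and confirmed eligibility, so the 52-in-2-years feasibility rule can be met with fewer than 52 randomised

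*Combined protocol and SAP*

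**What the plan says.** Section 3.3 makes the time to enrol 52 patients the primary outcome. Section 7.1 defines the event: "Enrollment in the trial will be defined as documentation of informed consent for patients approached". The decision rule follows directly: "If the study is unable to enroll 52 patients in a 2 year enrolment period", the design is judged not feasible. Section 8.1 states the same rule in positive form, adds that there are two sites, and does not define enrolment.

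Other sections use the word for a later step:

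- Section 5.3.1: after consent, bloodwork is done "if it has not been performed in the past 2 weeks". Eligibility is then determined, and "If the eligibility is confirmed, then the patient will be enrolled (assigned a study ID) and randomized".
- Section 5.3.3.4: "Once enrolled, patients will be randomized to either the daily, or every other day treatment arm".
- Appendix C, Table 1: the row "Patient (surrogate) informed consent" and the row for the eligibility criteria are both marked in the column before enrolment. Randomisation is marked in the column after it.

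Section 5.1 ties the 52 to randomisation, with 26 patients in each arm. Section 8.2 bases the intention-to-treat analysis on the patients randomised.

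**The concern.** Enrolment cannot be the act of consenting and also a step that follows consent and an eligibility check. The two definitions count different people whenever someone consents and is then found ineligible, and the protocol does not say which count decides feasibility.

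This is the only numeric go/no-go rule in the protocol, and it determines whether the design goes forward to a definitive trial. Counted at consent, the pilot could be declared feasible although fewer than 52 patients were randomised. If the choice of definition stays open until the counts are known, it could also be made after the fact. The trigger for the interim analysis in 8.3, set at 20 enrolled, has the same ambiguity.

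**Working it through.** **1. What the 52 stands for.** Inputs from section 8.1, Table 2 and its notes: true difference 0, SD 5 g/L, margin 5 g/L, one-sided 95% confidence bound, power 90%, dropout 30%.

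- Per arm: 2 × (1.645 + 1.282)² × 5² / 5² = 17.1, rounded up to 18. The total is 36, which matches Table 2.
- With dropout: 36 / 0.70 = 51.4, rounded up to 52, which also matches.

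The 52 therefore allows for dropout only. It has no allowance for loss between consent and randomisation. Together with 26 per arm in section 5.1, this means that 52 is a number of randomised patients.

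**2. Order of events.**

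| Source | Where enrolment falls |
|---|---|
| 7.1 | At documented consent |
| 5.3.1 | After consent, at confirmed eligibility and study ID; randomisation follows |
| 5.3.3.4 | Before randomisation |
| Appendix C | After consent and eligibility check, before randomisation |

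The last three agree with each other. Section 7.1 stands alone.

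**3. Size of the gap.** Let s be the share of consenting patients who are never randomised. The documents give no value, so s is assumed to be 0, 5, 10 or 20%.

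- Randomised from 52 consents = 52 × (1 − s).
- Consents needed for 52 randomised = 52 / (1 − s), rounded up.

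**4. When the verdict changes.** Assume steady accrual, with the 52nd consent at month T and a lag of L months from consent to randomisation. The consent count passes if T ≤ 24. The 52nd randomisation falls at T / (1 − s) + L, so the randomised count passes if T ≤ (24 − L)(1 − s). The verdicts differ when T lies between (24 − L)(1 − s) and 24.

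For L, the closest figure in the documents is the heading of 5.4.1.1, which puts screening and enrolment within 1 week of randomisation. Taking 7 days gives L = 0.23 month. Applying that figure to the time from consent to randomisation is an assumption.

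| s | Randomised from 52 consents | Consents needed for 52 randomised | Window, L = 0 (months) | Window, L = 0.23 (months) |
|---|---|---|---|---|
| 0% | 52 | 52 | 0 | 0.2 |
| 5% | 49.4 | 55 | 1.2 | 1.4 |
| 10% | 46.8 | 58 | 2.4 | 2.6 |
| 20% | 41.6 | 65 | 4.8 | 5.0 |

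For example, at s = 10% and L = 0 the limit is 24 × 0.90 = 21.6 months, so the window is 24 − 21.6 = 2.4 months. With L = 0.23 it is 24 − 23.77 × 0.90 = 2.6 months.

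**The case against.** The strongest reply is that few patients should be lost after consent. Study staff review the history and the standard-of-care bloodwork first, and section 5.3.1 says "Patients interested in participating and meeting both inclusion and no exclusion criteria will be given an Informed Consent Form". New bloodwork is needed only when none is recent, and 5.4.1.2 lets screening bloods serve as the baseline. No passage supports a failure rate of 10% or 20%. All of this stands, and it limits the size of the effect. It does not remove the conflict, because 5.3.1 still places the eligibility decision after consent.

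A second reply is that 8.1 keeps the trial running until at least 36 patients complete it, so the number of analysable patients is protected. That also stands, but the condition governs when the trial ends. It is not part of the feasibility rule.

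Three stronger readings are tempting, and the documents do not support them:

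- A reader might infer that the pilot will be wrongly declared feasible. Without a post-consent failure rate, the text shows only that this can happen.
- A reader might take section 4.0, which speaks of 52 patients completing the trial, as a rival target. Its next sentence applies 30% dropout and leaves 36, so 52 is the count before dropout and the phrase is loose wording.
- A reader might conclude that enrolment should be defined as randomisation. That would contradict 5.3.3.4 and Appendix C, which put enrolment first.

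**Conclusion.** The inconsistency is certain: section 7.1 conflicts with 5.3.1, 5.3.3.4 and Appendix C on the event that the primary outcome counts, and with the meaning of 52 in section 5.1 and Table 2. Read literally, the rule in 7.1 and 8.1 can be met with fewer than 52 randomised.

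The practical effect is conditional. It needs failures or delay after consent, and a 52nd consent late in the 24 months. With no failures and no lag it is nil, and at the assumed 20% failure rate the critical period is about 5 months. These windows rest on steady accrual and on assumed failure rates and lag. Counting at consent would not be invalid in itself. The fault is that the protocol holds two definitions and applies its only numeric feasibility rule to the one that does not match the target. This should be corrected, but it does not undermine the design.

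**What to change.** - In 7.1, delete the consent definition and use that of 5.3.1: eligibility confirmed and study ID assigned.
- In 7.1 and 8.1, state the feasibility target as 52 patients randomised within 2 years at two sites. The order of enrolment then randomisation in 5.3.3.4 and Appendix C stays as it is.
- Report patients who consented but were not randomised as a separate count. The source already exists: "A recruitment log of eligible and ineligible patients as well as reasons for non-consent will be kept at each participating centre".

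Two minor wording points can be reconciled at the same time and are not part of the main claim. One is the reference to completing the trial in section 4.0. The other is in 7.2, items 3 to 5, where the titles refer to treated patients but the formulas appear to divide by consenting patients. The fraction lines are lost in the text available here, so that denominator is inferred.

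The cost is wording only, with no new data. The one drawback is that the feasibility result may look slightly less favourable if some consenting patients prove ineligible.

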7.2 Secondary outcome assessments

Feasibility

1. Proportion of eligible patients consenting to participate

$$\frac{\# \text{ meeting eligibility criteria} - \# \text{ in whom consent not obtained}}{\# \text{ meeting eligibility criteria}}$$

2. Proportion of consenting patients receiving the allocated treatment

consenting to treatment - # not administered allocated treatment
consenting to treatment

3. Proportion of treated patients completing 4 week and 12 week laboratory tests

completing 100% of 4 week and 12 week lab tests
consenting to treatment

4. Proportion of treated patients completing 4 week, 8 week and 12 week side effect questionnaire

completing 100% of 4 week, 8 week and 12 week side effect questionnaire
consenting to treatment

5. Proportion of treated patients completing 4 week, 8 week and 12 week FACIT-fatigue scale

completing 100% of 4 week, 8 week and 12 FACIT-fatigue scale
consenting to treatment

6. Proportion of treatment doses taken as per protocol based on pill count

$$\frac{\text{total # of doses} - \text{# of missed doses}}{\text{total # of doses}}$$

7. Proportion of treated patients taking at least 90% of their prescribed doses

$$\frac{\text{# of patients taking at least 90% of prescribed doses}}{\text{total # of treated patients}}$$

8. Proportion of treated patients requiring a step down in therapy

$$\frac{\text{# of patients requiring step down in therapy}}{\text{total # of treated patients}}$$

Clinical/Safety

9. Hemoglobin increment at 4 and 12 weeks is defined as the 4 or 12 week hemoglobin value minus the baseline hemoglobin value

10. Proportion with complete hemoglobin response defined as hemoglobin greater than or equal to 120 g/L in women; and 130 g/L in men at 4 weeks and 12 weeks

11. Change in reticulocyte count at 4 and 12 weeks defined as the 4 or 12 week reticulocyte count minus the baseline reticulocyte count

12. Change in ferritin, serum iron and TSAT at 12 weeks defined as the value at 12 weeks minus the baseline value

13. Quality of life (FACIT-fatigue scale) at 4, 8 and 12 weeks

14. Proportion with side effects and type of side effects at 4, 8 and 12 weeks as determined by the oral iron side effect questionnaire
15. Proportion of patients who stop taking oral iron due to side effects at 4 and 12 weeks
16. Need for escalation in therapy (increase in oral iron regimen from every other day to daily, need for intravenous iron, need for transfusion, visit to emergency department related to anemia) assessed at 12 weeks
17. Proportion of patients with a drop in hemoglobin of 10 g/L or more at weeks 4 and 12

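### Item 1 of section 7.2 takes consent among patients who meet the criteria, but some patients are tested only after they consent, so untested decliners may never enter the denominator

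*Combined protocol and SAP*

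**What the plan says.** Section 7.2, item 1, is the "Proportion of eligible patients consenting to participate". Its formula takes the number "meeting eligibility criteria", subtracts the number "in whom consent not obtained", and divides by the first number. There is no rule for a patient whose eligibility was never established.

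The last part of section 5.3.1 sets the order of steps for patients who lack results from the preceding 2 weeks: "Once the patient has consented, bloodwork will be performed at the participating institution's laboratory or at a local lab". Only after those results are in does the site settle whether the criteria are met, and the step that follows is: "If the eligibility is confirmed, then the patient will be enrolled (assigned a study ID) and randomized". Hemoglobin and ferritin are inclusion criteria (5.2.1) and creatinine clearance is an exclusion criterion (5.2.2), so this bloodwork can decide eligibility.

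The opening of section 5.3.1, repeated in 11.2, describes a different order: standard-of-care bloodwork is reviewed first, and the consent form goes to patients who already satisfy the criteria.

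The recruitment log in 5.3.1 has two classes, eligible and ineligible. The case logs in 5.4.1.1 are opened for referrals that meet the inclusion criteria and record why eligible patients did not consent. Section 11.2 treats anyone who declines as a screening failure.

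**The concern.** On the route where bloodwork follows consent, a patient who agrees is tested and then counted as eligible or not. A patient who refuses is not tested, because consent must come before any study procedure. Being counted in the denominator therefore depends partly on having consented. A proportion built this way is conditioned on its own outcome and tends towards 100% as the untested share grows.

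This is the first secondary feasibility outcome of a pilot, and section 8.2 promises feasibility proportions with 95% confidence intervals to inform the definitive trial. The interval covers sampling error only and cannot show that some decliners are missing from the denominator. Without a counting rule, two sites could also treat the same untested decliner differently.

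**Working it through.** The plan states no expected consent proportion and no number to be approached, so there is no figure to reproduce. The size has to be shown over assumed values.

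**Assumptions (none from the documents).**
- c: true consent rate, set at 0.60.
- u: share of approached patients whose eligibility is untested at approach: 0.10, 0.25 or 0.50.
- e: share of untested patients who are truly eligible: 0.5 to 0.8.
- Consent is independent of eligibility, and patients with recent results who are approached are all eligible.

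**Counts per 1,000 approached.**
- Tested beforehand, consenting: 1000(1−u)c.
- Tested beforehand, declining: 1000(1−u)(1−c).
- Untested, consenting and later found eligible: 1000·u·e·c.
- Untested, declining, never classified: 1000·u(1−c).

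**Formulas.** The numerator in both cases is the count of confirmed eligible consenters.
- Untested decliners dropped (that is, treated as all ineligible): c(1−u+ue) / (1−u+uec).
- Untested decliners all counted as eligible: c(1−u+ue) / (1−u+uec+u(1−c)).

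**Worked case, u = 0.25, e = 0.5.** The four counts are 450, 300, 75 and 100. Dropped: (450+75)/(450+300+75) = 525/825 = 0.636. All counted as eligible: 525/(825+100) = 525/925 = 0.568.

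| u | e | Dropped | All counted as eligible |
|---|---|---|---|
| 0.10 | 0.5 | 570/930 = 0.613 | 570/970 = 0.588 |
| 0.10 | 0.8 | 588/948 = 0.620 | 588/988 = 0.595 |
| 0.25 | 0.5 | 525/825 = 0.636 | 525/925 = 0.568 |
| 0.25 | 0.8 | 570/870 = 0.655 | 570/970 = 0.588 |
| 0.50 | 0.5 | 450/650 = 0.692 | 450/850 = 0.529 |
| 0.50 | 0.8 | 540/740 = 0.730 | 540/940 = 0.574 |

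Against the true 0.60, dropping overstates by 1.3–2.0, 3.6–5.5 and 9.2–13.0 points at the three untested shares. Counting all as eligible understates by 0.5–1.2, 1.2–3.2 and 2.6–7.1 points. At u = 0 both formulas return c exactly.

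**Other consent rates, u = 0.25.** With true consent of 0.40, dropping gives 0.438–0.458. With 0.80 it gives 0.824–0.835.

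**Check of the proposed measure.** In the worked case, consenters over all approached is (450+150)/1000 = 0.60, and the share of consenters confirmed eligible is 525/600 = 0.875. The two figures keep willingness and eligibility apart.

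**The case against.** The strongest reply is that the main recruitment text screens first. Sections 5.3.1 and 11.2 have standard-of-care bloodwork reviewed before the consent form is given. For those patients the formula works as written. This stands, and it confines the problem to patients without bloodwork in the past 2 weeks. It does not remove the later text of 5.3.1, which settles eligibility after consent for them. Appendix C does not decide the matter either, since consent, criteria and laboratory tests all sit in the column before enrolment.

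Second, absence of results in the past 2 weeks is not absence of any results. Some of these patients will have older qualifying values, and deferred blood donors are sent to their family physician for investigation before any referral. This also stands: such decliners may go unclassified, but not all will. Donors who contact a site directly are the likelier gap, and their share is not given.

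Third, the error may be small beside sampling error. With 75–100 patients and a proportion near 50%, the 95% half-width is 1.96·√(0.25/n), about 10–11 points. That is fair when few are untested, less so at 50% untested.

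A reader might also infer that the formula subtracts every non-consenter, tested or not, from the confirmed eligible count. That would give 0.515–0.540 at u = 0.25 and could turn negative at larger u. The documents do not support it: the outcome is labelled as a proportion of eligible patients, and 5.4.1.1 logs non-consent among eligible patients.

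**Conclusion.** The point holds in a limited form. Item 1 is sound for patients whose eligibility is known before they are asked. For those tested only after consent, decliners may never be classified, and the formula is then conditioned on consent. If they are dropped, the overstatement is about 1–2 points at 10% untested, 4–6 at 25% and 9–13 at 50%, given 60% true consent, 50–80% of untested patients eligible, and consent independent of eligibility. The untested share is not in the documents, so the actual size cannot be stated, and it is zero if all have recent results.

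A reader might infer that the trial's feasibility decision is affected, or that this proportion sets the forecast for the definitive trial. The documents say neither. Feasibility is judged on enrolling 52 patients in 2 years (7.1, 8.1), which does not use this denominator, and item 1 carries no threshold.

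**What to change.** Define item 1 as consenters divided by all approached patients judged potentially eligible at approach, whether they consent or decline. Report separately the proportion of consenters who were confirmed eligible and randomized. Section 7.1 already defines enrollment with reference to patients approached, so the new denominator suits the plan's own terms.

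Add a category for eligibility not determined to the recruitment log. The log now separates only eligible from ineligible patients, so it cannot be assumed to hold the needed counts. If the figure among eligible patients is kept, report it with bounds that treat untested decliners as all ineligible and then as all eligible (0.636 and 0.568 in the worked case). Reconcile the order of screening and consent in the opening of 5.3.1 and in 11.2 with the later text of 5.3.1.

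The cost is one redefined formula, one log field and a slightly different estimand: consent among potentially eligible rather than confirmed eligible patients. The two coincide only if consent does not depend on eligibility. No extra patients or procedures are needed.
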